6. STUDY OBJECTIVES

The overall objectives of the study are to assess the efficacy and safety of a single administration of STAP-001 in subjects with epilepsy with a predictable seizure pattern.

The primary objectives are:

- To assess the efficacy of STAP-001 (1.0 mg and 2.0 mg) compared to placebo in treating a seizure episode
- To assess the clinical feasibility and safety of the inhalation of STAP-001 (1.0 mg and 2.0 mg) compared to placebo in subjects during a seizure episode
- To assess the sedation associated with administration of STAP-001 (1.0 mg and 2.0 mg) compared to placebo

This document cannot be used to support any marketing authorization application and any extensions or variations thereof.

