By subject listings will be provided for any deaths, serious adverse events, and adverse events leading to discontinuation of treatment.

Sedation Assessment

Sedation as measured by the dichotomous using a 100-mm linear VAS will be summarized by time point.

Clinical Laboratory

Clinical laboratory variables will be presented in 2 ways. First, change from Baseline to each scheduled assessment will be summarized descriptively. Baseline will be defined as the laboratory value obtained before the first dose of study drug on Day 1; if Day 1 values are unavailable, then values obtained at the Screening Visit will be used.

Second, treatment-emergent potentially clinically significant (PCS) laboratory values will be identified. Potentially clinically significant values are defined as those that meet Grade 3 or Grade 4 toxicity criteria from the CTCAE criteria. Treatment-emergent PCS laboratory values are those in which the baseline value is not PCS and the post-baseline value is PCS. The number and percentage of subjects with treatment-emergent PCS laboratory values will be summarized by treatment group for each clinical laboratory variable.

Vital Signs

The mean change from baseline to each scheduled assessment will be summarized descriptively by treatment group for each vital sign variable specified in this protocol.

Baseline will be defined as the last vital sign value obtained before the first dose of study drug on Day 1; if Day 1 values are unavailable, then values obtained at the Screening Visit will be used.

Electrocardiogram

The change from baseline in electrocardiogram intervals (PR, QT, QTcF, QRS, and RR) to each scheduled assessment will be summarized descriptively by treatment group.

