^d At timepoint 0 (+2 min), and 10 (±2 min), 30 (±2 min) and 60 (±5 min) minutes, 2 (±5 min) and 6 (±5 min) hours after the dosing of the study drug.

^e Attached at Entry into CRU/EMU

^f At 6 (±5 min) hours after the dosing of the study drug.ⁱ

^g When multiple procedures are scheduled at the same time point, the VAS assessment should be performed first, immediately followed by the PK draw. Collected at timepoints 10 (±2 min), 30 (±2 min) and 60 (±5 min) minutes, 2 (±5 min) and 6 (±5 min) hours after the dosing of the study drug.

	Qualification Phase			Treatment Phase	Exit Procedures ^a	Follow-up Phone Call
	Screen Visit	Qualification Period ^b	Qualification Visit			
Procedures	Day -35 (May extend to Day -63)	Day -35 to Day -8 (May extend to Day -63)	Day -7 to Day -1	Day 1 up to Day 8		14 ±2 days from Study Drug Administration
Dispense and begin Seizure Diary	X			X ^h		
Seizure Diary Completion		X		X		
Seizure Diary Collection and Review			X	X		
12-Lead ECG	X			X ^c	X	
Chemistry, hematology and urinalysis	X			X ^c	X	
Urine drug screen ⁱ	X			X ^c		
Urine Pregnancy test (if applicable)	X			X ^c		
PK Sample collection				X ^j		
Device training	X			X ^c		
EEG Recording				X ^{ek}		
Study drug administration^l				X		
Adverse event assessment ^m	X	X	X	X	X	X
Subject seizure events forms sent to Epilepsy Study Consortium Review Board	X ⁿ					
Completed seizure diary sent to Medical Monitor for review			X			

^h Staff Caregiver completes the seizure diary during the Treatment Phase

ⁱ Drug Screen needs to be negative to allow entry into the CRU/EMU and dosing of the study drug.

^j PK samples will be collected at 10 (±2 min), 30 (±2 min) and 60 minutes (±5 min), 2 hours (±5 min) and 6 hours (±5 min) after the dosing of the study drug. If the PK sample is drawn outside of the timeframe, the sample will still be collected and evaluated.

^k Video EEG Recording will be throughout the subject's stay at the CRU/EMU

^l At the onset of the predictable seizure

^m Adverse Events will be collected throughout the study after Informed Consent is signed and through Follow-Up

ⁿ Forms completed and sent to review board within 48 hours after the subject or the subject's LAR signs informed consent at the Screening Visit.

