#### Primary Efficacy Endpoint

The primary efficacy endpoint will be the proportion of responders in each treatment group achieving seizure activity cessation within 2 minutes after the administration of the study drug and no recurrence of seizure activity within 2 hours. The primary endpoint will be analyzed with a chi-squared test. The overall treatment comparison, as well as pair-wise comparisons between each dose level and placebo will be performed. The estimates of the treatment difference versus placebo and their 95% confidence interval will be presented.

There will be no adjustment for multiple treatment group comparisons in this dose-ranging Phase 2b study. The dose-response relationship will be explored with a regression analysis.

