### 3.3.3 Safety Analysis

All safety summaries will be descriptive with no statistical hypothesis testing and based on the Safety Population. Subjects will be summarized according to the study drug received. (i.e., as treated), should it differ from the randomized treatment arm. All safety endpoints will be listed in by-subject data listings.

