#### Sedation Assessment

- Sedated and alert scale as measured using a 100-mm linear VAS will be summarized by time point.
- Sleepy and Awake scale as measured using a 100-mm linear VAS will be summarized by time point.

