#### 4.1.2 Summary of Efficacy Endpoints

Table 14.2.1.1 Result of Treatment Response – mITT Population

Table 14.2.1.2 Result of Treatment Response – PP Population

Table 14.2.2.1 Results of Seizure Episode Severity Scale – mITT Population

Table 14.2.2.2 Results of Seizure Episode Severity Scale – PP Population

Table 14.2.3.1 Result of Use of Rescue Medication – mITT Population

Table 14.2.3.2 Result of Use of Rescue Medication – PP Population

Table 14.2.4.1 Result of Secondary Generalization Evolution – mITT Population

Table 14.2.4.2 Result of Secondary Generalization Evolution – PP Population

Table 14.2.5.1 Summary of Seizure Number after Study Drug Administration – mITT Population

Table 14.2.5.2 Summary of Seizure Number after Study Drug Administration – PP Population

Table 14.2.5.3 Treatment Comparison of Seizure Number after Study Drug Administration – mITT Population

Table 14.2.5.4 Treatment Comparison of Seizure Number after Study Drug Administration – PP Population

Table 14.2.6.1 Kaplan-Meier Analysis of Time to Next Seizure Event after Study Drug Administration – mITT Population

Table 14.2.6.2 Kaplan-Meier Analysis of Time to Next Seizure Event after Study Drug Administration – PP Population

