#### **4.1.4 Summary of Safety Endpoints**

Table 14.3.1.1 Summary of Adverse Events – Safety Set

Table 14.3.1.2 Summary of Adverse Events by MedDRA System Organ Class and Preferred Term – Safety Set

Table 14.3.1.3 Summary of Serious Adverse Events by MedDRA System Organ Class and Preferred Term – Safety Set

Table 14.3.1.4 Summary of Adverse Events by Severity, MedDRA System Organ Class and Preferred Term – Safety Set

Table 14.3.1.5 Summary of Adverse Events by Relationship to Study Agent, MedDRA System Organ Class and Preferred Term – Safety Set

Table 14.3.1.6 Summary of Adverse Events by MedDRA Preferred Term and Overall Frequency – Safety Set

Table 14.3.2.1 Summary of Vital Signs by Time Point – Safety Set

Table 14.3.2.2 Summary of Vital Signs Change from Baseline by Time Point – Safety Set

Table 14.3.3.1 Summary of ECG by Time Point – Safety Set

Table 14.3.3.2 Summary of ECG Change from Baseline by Time Point – Safety Set

Table 14.3.3.3 Summary of ECG Category Results by Time Point – Safety Set

Table 14.3.3.4 Summary of ECG Interpretation by Category and Time Point – Safety Set

Table 14.3.4.1 Summary of Physical Examination by Visit – Safety Set

Table 14.3.4.2 Summary of Neurological Examination by Visit – Safety Set

Table 14.3.5.1 Summary of Laboratory (Hematology) Test Results – Safety Set

Table 14.3.5.2 Summary of Laboratory (Blood Chemistry) Test Results – Safety Set

Table 14.3.5.3 Summary of Laboratory (Urine) Continuous Test Results – Safety Set

Table 14.3.5.4 Summary of Laboratory (Urine) Category Test Results – Safety Set

Table 14.3.5.5 Number and Percentage Subjects with TEPCS Laboratory (Hematology) Test Results – Safety Set

Table 14.3.5.6 Number and Percentage Subjects with TEPCS Laboratory (Blood Chemistry) Test Results – Safety Set

Table 14.3.5.7 Number and Percentage Subjects with TEPCS Laboratory (Urine) Test Results – Safety Set

Table 14.3.5.8 Number and Percentage Subjects with Abnormal Laboratory (Hematology) Test Results – Safety Set

Table 14.3.5.9 Number and Percentage Subjects with Abnormal Laboratory (Blood Chemistry) Test Results – Safety Set

Table 14.3.5.10 Number and Percentage Subjects with Abnormal Laboratory (Urine) Continuous Test Results – Safety Set

Table 14.3.6.1 Summary of Sedation and Alert Scale VAS – Safety Set

Table 14.3.6.2 Summary of Sleepy and Awake Scale VAS – Safety Set

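### Sedation compared with placebo is a primary objective, but the SAP text plans only by-group VAS summaries, with no dose-minus-placebo difference or confidence interval

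*SAP*

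**What the plan says.** Protocol 6 and SAP 1.1 both list among the primary objectives: "To assess the sedation associated with administration of STAP-001 (1.0 mg and 2.0 mg) compared to placebo". The protocol synopsis gives the same objective without the comparison to placebo.

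The analysis text is shorter. SAP 3.3.3, Sedation Assessment, states "Sedated and alert scale as measured using a 100-mm linear VAS will be summarized by time point" and repeats this for the Sleepy/Awake scale. Protocol 13.4.4 reads "Sedation as measured by the dichotomous using a 100-mm linear VAS will be summarized by time point". SAP 3.3.3 opens with the rule "All safety summaries will be descriptive with no statistical hypothesis testing", applied to the Safety Population with subjects grouped as treated. SAP 3.1 defines a continuous summary as n, mean, SD, median, minimum and maximum, by treatment group and time point. The sedation outputs in SAP 4.1.4 are Table 14.3.6.1, "Summary of Sedation and Alert Scale VAS", and its counterpart for the other scale, Table 14.3.6.2. SAP 4.3 lists no sedation figure.

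For the primary efficacy endpoint, by contrast, SAP 3.3.1 states "The estimates of the treatment difference versus placebo and their 95% confidence interval will be presented". The exploratory seizure counts have their own comparison outputs, such as "Table 14.2.5.3 Treatment Comparison of Seizure Number after Study Drug Administration".

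**The concern.** An objective worded as a comparison with placebo calls for an estimate of that comparison and a statement of its uncertainty. The text plans neither. A primary objective would then be reported in less detail than an exploratory count.

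This matters for dose choice. Protocol 4.4.2 and 7.3.1 describe a photosensitivity effect that looked similar at 1 mg and 2 mg, with sedation somewhat greater and longer at 2 mg. How much more sedation than placebo each dose produces is therefore one of the main things a dose-ranging study should report.

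The population is a second, smaller issue. SAP 2.1 puts the open-label Part 1 subjects, all on 1 mg, into the Safety Population. They know they inhaled alprazolam and they rate themselves. If they sit in the 1 mg column, that column set against placebo is not a randomised contrast.

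**Working it through.** **Is a comparison planned anywhere?** SAP 3.1, SAP 3.3.3, Protocol 13.4.4 and the titles of Tables 14.3.6.1 and 14.3.6.2 all describe summaries. SAP 3.1 fixes confidence intervals at two-sided 95%, but that sets the level of intervals called for elsewhere and does not call for one on the VAS. SAP 3.7 declares no change from the protocol analysis. The shells (SAP section 6) appear only as a heading in the supplied text.

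**Which contrast do the data allow?** Appendix 1A, note g, schedules the VAS after dosing: "Collected at timepoints 10 (±2 min), 30 (±2 min) and 60 (±5 min) minutes", then at 2 and 6 hours. Neither schedule has a VAS at unit entry or at time 0, so change from baseline is not available. The between-arm difference in post-dose values is the natural estimate. Rescue may be given once an episode has lasted 5 minutes after dosing (SAP 1.2.2), before the first VAS at 10 minutes. The difference is therefore a total effect of assignment to a dose, not the drug's own sedation.

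**Number per arm.** The documents give no sample size, power or precision figure for sedation. Their only such figure is 35 evaluable per arm for 57% against 20% responders, two-sided 0.05, 90% power (SAP 2.3). With pooled variance and mean rate 0.385:

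- n = [1.960 × √(2 × 0.385 × 0.615) + 1.2816 × √(0.57 × 0.43 + 0.20 × 0.80)]² / 0.37²
- n = (1.349 + 0.816)² / 0.1369 = 34.2, rounded up to 35

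This agrees with the plan; power at 35 per arm is 90.7%. The figure is sound and serves below only as the number per arm.

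**Precision of the missing estimate.** Half-width = t(0.975, 2n − 2) × SD × √(2/n). The SD is assumed to be 20 to 30 mm.

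- n = 35, t = 1.9955, SD 20: 1.9955 × 20 × √(2/35) = 9.5 mm
- n = 35, SD 30: 1.9955 × 30 × √(2/35) = 14.3 mm
- If only 28 of 35 can complete the VAS (an assumed 80%), t = 2.0049: 10.7 mm (SD 20) and 16.1 mm (SD 30)

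**Part 1 share of the 1 mg column.** Protocol 7.1 expects about nine subjects enrolled to give at least eight evaluable. If pooled with 35 randomised subjects, they are 8/43 = 18.6% to 9/44 = 20.5% of the column. If open-label ratings differed by an assumed 10 to 20 mm, the column mean would move by 0.186 × 10 = 1.9 mm to 0.205 × 20 = 4.1 mm, which is less than the half-widths above. The 2 mg contrast with placebo is not touched.

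**Is pooling certain?** No. SAP 2.1 includes Part 1 in the Safety Population, SAP 3.6 defines that population without naming either part, and the heading of SAP section 4 limits the outputs to the blinded phase.

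**Number of intervals.** 2 scales × 5 time points × 2 doses = 20. At the 5% level, 20 × 0.05 = 1 would be expected to exclude zero if there were no effect.

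**The case against.** The best defence is that this is a consistent choice. Both documents class sedation as a safety measure, both keep safety descriptive, and they agree on the VAS analysis. Summaries by group set each dose beside placebo, which is one way to assess a comparison. The objective on feasibility and safety also refers to placebo, and its safety part is likewise only summarised. The seizure-count tables report an efficacy endpoint with a named test, so they are not a strict precedent.

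Much of this stands. It is an omitted estimate, not a contradiction between protocol and SAP or a wrong number. No hypothesis test is owed. But the rule excludes testing; it does not exclude a descriptive difference with an interval.

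A second defence is that the contrast can be recovered. If the columns hold Part 2 subjects only, n, mean and SD are enough. If Part 1 is pooled, Listings 16.16 and 16.17 (both scales) with Listing 16.18 (randomisation) let a holder of the study report rebuild it. That is true, and it lowers the importance, but a primary objective should not depend on readers working from listings.

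Third, because the shells are not available here, a difference column cannot be ruled out. The claim is therefore limited to the supplied text and titles, which give no sign of one.

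A reader might also infer a known bias in millimetres from the 37-point gap in assumed non-response (80% on placebo, 43% on active). The documents do not support that. Non-response includes seizures that stopped and then recurred at any time up to 2 hours (SAP 3.6), so it need not mean a long seizure or rescue before an early VAS. The total-effect caveat stands, but no figure can be put on it.

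**Conclusion.** The point holds as a gap between objective and analysis. The supplied SAP text plans no dose-minus-placebo difference and no interval for a comparison that Protocol 6 and SAP 1.1 call primary, and it leaves unclear whether open-label subjects enter the 1 mg column.

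The estimate left out would have a half-width of about 9.5 to 14.3 mm with 35 readings per arm. That range rests on an assumed SD of 20 to 30 mm and would be wider with missing VAS readings. It describes what would go unreported; printing the interval does not change the precision of the trial.

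Stronger readings fail. The sedation comparison is not impossible, since the data will exist. Pooling of Part 1 is not established. The sample size and the primary efficacy analysis are not affected. Importance is minor to moderate.

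**What to change.** In SAP 3.3.3, for each VAS and each post-dose time point, report the mean difference of each dose from placebo with a 95% CI in Part 2 subjects only, and show Part 1 in a separate column. In addition:

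- Label the differences descriptive, unadjusted and a total effect. State the direction: under Protocol 11.7 a lower value means more impairment.
- State whether arms are as treated, which is the SAP's safety rule, or as randomised.
- Name one key time point or one summary over the five time points before unblinding.
- Beside each difference, give by arm the number with a VAS and the number who had received rescue by then. Protocol 10.3 already requires the time of each concomitant medication.

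The cost is SAP wording, extra rows in two tables and one extra column, with no new data or subjects. The drawback is 20 unadjusted intervals, about one of which would exclude zero by chance if there were no effect; hence the label and the named key measure. If pooling was intended, the 1 mg column loses 8 to 9 subjects, who are still shown separately.

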#### Clinical Laboratory

Clinical laboratory variables will be presented in 3 ways.

1. Change from Baseline to each scheduled assessment will be summarized descriptively. Baseline will be defined as the laboratory value obtained before the first dose of study drug on Day 1; if Day 1 values are unavailable, then values obtained at the Screening Visit will be used.
2. The number and percentage of subjects with abnormal laboratory values will be summarized by treatment group for each clinical laboratory variable.
3. The number and percentage of subjects with treatment-emergent potentially clinically significant (PCS) laboratory values will be summarized by treatment group for each clinical laboratory variable. Potentially clinically significant lab values are defined as those that toxicity grade are  $\geq 3$  from the common terminology criteria for adverse events (CTCAE) criteria (See Section 7 Appendix). Treatment-emergent PCS laboratory values are those in which the baseline value is not PCS and the post-baseline value is PCS.

### **Vital Signs**

The mean change from baseline to each scheduled assessment will be summarized descriptively by treatment group for each vital sign variable specified in this protocol.

Baseline will be defined as the last vital sign value obtained before the first dose of study drug on Day 1; if Day 1 values are unavailable, then values obtained at the Screening Visit will be used.

### **Electrocardiogram**

The change from baseline in ECG intervals (PR, QT, QTcF, QRS, and RR) to each scheduled assessment will be summarized descriptively by treatment group.

### **Neurological and Physical Examinations**

- The number (%) of subjects of baseline neurological and physical examination results will be provided by categories of Normal/Abnormal/Not Done and treatment group for each examination item.
- The number (%) of subjects of post-baseline results will be summarized by categories of Normal/Abnormal/Not Done/No Change and treatment group for each examination item at scheduled assessment.

#### **3.3.4 Multiplicity Adjustment**

- Multiplicity adjustment will not be applied for multiple testing in this study.

### **3.4 Handling of Missing Data**

#### **3.4.1 Imputation Rules for AE Records**

For safety analyses, the incomplete date and time for the safety events will not be imputed. However, the following imputation rule will be applied for AEs.

- If the start date of an AE is missing, then the AE will be considered as Treatment-Emergent AE (TEAE).

- If the end date of an AE is missing and the ongoing flag is missing, then the AE status will be considered as ongoing.
- If the severity of an AE is missing, then the AE will be considered as “Severe” (CTCAE grade 3).
- If the relationship to the study agent of an AE is missing, then the AE will be considered as “related” to study agent.

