12. ADVERSE EVENTS

12.1.1. Definition of Adverse Event

An adverse event is any untoward medical occurrence that may appear or worsen in a subject during the course of a study. It may be a new intercurrent illness, a worsening concomitant illness, an injury, or any concomitant impairment of the subject's health, including laboratory test values, regardless of etiology. Any worsening (ie, any clinically significant adverse change in the frequency or intensity of a pre-existing condition) should be considered an adverse event. A diagnosis or syndrome should be recorded on the adverse event page of the eCRF rather than the individual signs or symptoms of the diagnosis or syndrome. A worsening of the condition under study will not be reported as an adverse event.

All subjects will be monitored for adverse events during the study. Assessments may include monitoring of the following parameters: the subject's clinical symptoms, laboratory, physical examination findings, or findings from other tests and/or procedures.

An adverse event reported after informed consent and occurring before the first dose of study drug in the CRU/EMU, will be considered a pretreatment adverse event and will be captured on the eCRF. Adverse events will be considered treatment-emergent if the onset is after the first dose of study drug.

An abnormal laboratory value is considered to be an adverse event or a component of an adverse event if the abnormality:

- results in discontinuation from the study;
- is judged by the Investigator to be of significant clinical importance requiring treatment, modification/interruption of investigational product dose, or any other therapeutic intervention

Regardless of severity grade, only laboratory abnormalities that fulfill a seriousness criterion need to be documented as a serious adverse event.

If a laboratory abnormality is one component of a diagnosis or syndrome, then only the diagnosis or syndrome should be recorded on the adverse event eCRF. If the abnormality was not a part of a diagnosis or syndrome, then the laboratory abnormality should be recorded as the adverse event. If possible, the laboratory abnormality should be recorded as a medical term and not simply as an abnormal laboratory result (e.g., record thrombocytopenia rather than decreased platelets).

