12.1.2.4. Duration

For all adverse events whether or not considered serious, the Investigator will provide a record of the start and stop dates of the event. Every effort should be made to resolve all adverse events with continued follow-up with the subject until appropriate resolution can be achieved. If an event is unresolved at the end of the study it will be recorded as ongoing.

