#### Adverse Events

An adverse event reported after informed consent and occurring before the first dose of study drug in the CRU/EMU will be considered a pre-treatment adverse event. Treatment-emergent adverse events (TEAEs) will be defined as any adverse event that occurs after administration of study drug.

- The number and percentage of subjects who experience TEAEs will be summarized by treatment group for the following:
  - By system organ class and preferred term
  - By severity, system organ class, and preferred term
  - By relationship to study drug, system organ class, and preferred term
  - Serious adverse events by system organ class and preferred term
  - TEAE by preferred term and overall frequency.
- Subjects who report the same preferred term on multiple occasions will be counted once for the preferred term: under the highest severity when summarized by severity and under the closest relationship to study drug when summarized by relationship.
- If a subject reports multiple preferred terms for a system organ class, the subject will be counted only once for that system organ class.
- Subject listings will be provided for any deaths, serious adverse events, and adverse events leading to withdrawal.

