#### Important Derived Variables:

- Age (year) = (Screening Date – Date of Birth +1)/365.25.
- Duration of Seizure History (year) = (Screening Date – Epilepsy Onset Date +1)/365.25.
- Prior Medications and Treatments: the medications and treatments started before enrolled to the study without any change after the enrollment.
- Concomitant Medication and Treatments: the medications and treatments started on or after the time of the first dose of the study drug. Any medications and treatments started before but changed after the first dose of the study drug will be considered as concomitant medications and treatments.

- Baseline: All clinical measurements (safety and efficacy data) collected at Day 1 or before the first dose will be analyzed as baseline.
- Post Baseline: All clinical measurements (safety and efficacy data) collected after the first dose will be analyzed as post baseline.
- Treatment emergent Adverse Events (TEAE): Any AEs started on or after the time of the first study drug dosed.

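### SAP 3.4.1 makes any AE with a missing start date treatment-emergent without checking the stop date, so an AE recorded as over before dosing would be misclassified

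*SAP*

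**What the plan says.** SAP 3.4.1 (Imputation Rules for AE Records) first states that "the incomplete date and time for the safety events will not be imputed", then lists exceptions for adverse events. The one at issue is: "If the start date of an AE is missing, then the AE will be considered as Treatment-Emergent AE (TEAE"). The only bullet in that section that mentions the end date serves another purpose: "If the end date of an AE is missing and the ongoing flag is missing, then the AE status will be considered as ongoing". It sets ongoing status and plays no part in deciding treatment emergence.

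The definitions are elsewhere. SAP 3.3.3 (Adverse Events) says an event reported after consent and "occurring before the first dose of study drug in the CRU/EMU will be considered a pre-treatment adverse event". SAP 3.6 (Important Derived Variables) defines a treatment-emergent event as "Any AEs started on or after the time of the first study drug dosed". Protocol 12.1.1 agrees with SAP 3.3.3 and adds that an event before the first dose "will be considered a pretreatment adverse event and will be captured on the eCRF". Protocol 12.1.2.4 requires, for every adverse event, that "the Investigator will provide a record of the start and stop dates of the event".

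**The concern.** A worst-case rule for missing onset is meant for events whose timing is unknown. Here it also reaches events whose timing is known from another field. An event that stopped before dosing cannot have started after it, whatever the start-date field shows. For that record, the rule in SAP 3.4.1 and the definitions in SAP 3.3.3 and 3.6 give opposite answers, and a programmer following 3.4.1 literally would put a pre-treatment event into the treatment-emergent tables.

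What is at stake is the descriptive safety comparison. Safety against placebo is among the primary objectives (SAP 1.1), and SAP 3.3.3 tabulates treatment-emergent events by treatment group. A misplaced record counts an event that the study drug cannot have caused. In an active arm it inflates the apparent risk; in the placebo arm it narrows the difference from active drug. If severity or relationship is also missing on the same record, SAP 3.4.1 further sets it to severe or related.

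**Working it through.** The plan states no figure on this point, so there is nothing to reproduce. The check has two parts.

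**1. Can the record arise, and how is it classified?**

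- Pre-dose events are in the database: they are collected from consent and captured on the eCRF (Protocol 12.1.1, 12.1.5).
- Start and stop dates are separate items (Protocol 12.1.2.4), so one can be missing while the other is present.
- SAP 3.4.1 does not impute incomplete dates, so no other step uses the stop date to bound the onset.

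Set the first dose at day 0 and apply three rules: SAP 3.4.1 as written, the definitions in SAP 3.3.3 and 3.6, and SAP 3.4.1 with a stop-date exception.

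| Start | Stop | SAP 3.4.1 as written | Definitions | With exception |
|---|---|---|---|---|
| missing | day -10 | TEAE | pre-treatment | not TEAE |
| missing | day -1 | TEAE | pre-treatment | not TEAE |
| missing | day 0, no time | TEAE | open | TEAE |
| missing | day 3 | TEAE | open | TEAE |
| missing | missing | TEAE | open | TEAE |
| day -5 | day -2 | not TEAE | pre-treatment | not TEAE |
| day 1 | day 2 | TEAE | TEAE | TEAE |

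Only the first two rows conflict, and they are the only rows that the exception changes. In the three open rows the conservative assignment is reasonable and stays.

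**2. How much can one record move a table?**

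One extra subject with a term in a group of n changes that term's incidence by 100/n percentage points.

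- 35 evaluable per arm (SAP 2.3): 100/35 = 2.9 points.
- About 115/3 = 38 randomized per arm (SAP 2.3): 100/38 = 2.6 points.
- 1 mg group including Part 1: SAP 2.1 places both parts in the Safety Population, and Part 1 subjects receive 1 mg (SAP 1.2.1). If the 1 mg column pools them, with 8 to 9 from Part 1, n is 35 + 8 = 43 to 38 + 9 = 47. The change is then 100/43 = 2.3 to 100/47 = 2.1 points.
- Subject already counted for that term: 0, because SAP 3.3.3 counts a subject once per preferred term.

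These are per-record ceilings for a single term. The total effect depends on how many such records there are, and the documents do not give that number.

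**The case against.** The case for leaving the rule alone is fair. It is conservative, applies to all arms alike, over-counts rather than hides events, and fits the other worst-case defaults in SAP 3.4.1. Safety summaries carry no hypothesis tests, and every event is listed by subject (SAP 3.3.3). The affected record needs a missing start date, a stop date that is present, and a stop date before dosing. The protocol requires both dates (12.1.2.4, 12.1.5) and provides monitoring queries and programmed completeness checks (15.4, 15.5). All of this stands and limits the importance of the point. It does not remove the conflict: conservatism is an answer to unknown timing, and here the timing is known. Equal application across arms also does not ensure that a handful of records fall evenly.

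Three stronger readings are tempting, but the documents do not support them.

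- A reader might infer that a partial start date, such as one giving only a month before dosing, is also forced into the treatment-emergent tables. SAP 3.4.1 speaks of incomplete dates in one sentence and of a missing start date in the bullet, and SAP 3.4.2 separates completely missing from partial dates for epilepsy onset. On that usage the bullet does not reach partial dates. At most the SAP is silent on them.
- A reader might infer from the schedule that most events with missing onset are pre-treatment, since screening and qualification last up to 63 days and the follow-up call comes at 14 ± 2 days. That compares calendar time only. It does not measure the share of missing-start events, or of those with a pre-dose stop date. Events on active drug are also likely to cluster after dosing: Protocol 4.4.2 reports adverse events in 50 to 100% of healthy volunteers on STAP-001 against 10% on placebo.
- A reader might infer that the treatment-emergent tables will contain such events. That follows only if such records exist and survive data cleaning.

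**Conclusion.** Wrong as written, with minor consequence. For an adverse event with a missing start date and a recorded stop date before the first dose, SAP 3.4.1 contradicts SAP 3.3.3, SAP 3.6 and Protocol 12.1.1, and nothing in either document resolves it. This rests on reading the bullet literally and on the recorded stop date being correct.

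The effect is at most about 2.6 to 2.9 percentage points per record for one term in an arm of 38 to 35. It is about 2.1 to 2.3 points if the 1 mg group is pooled with Part 1 (assumed 47 to 43 subjects), and nil for that term's incidence if the subject already has it. The number of records is unknown and probably small. The efficacy analyses do not depend on the rule. The point is an error in a stated rule, not evidence of a material bias.

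**What to change.** Replace the bullet in SAP 3.4.1 with:

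> An AE with no recorded start date is treatment-emergent unless its recorded stop date (and time, if available) is before the first dose of study drug.

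Anchoring this to the first dose, rather than to the calendar day of dosing, keeps it in line with SAP 3.6, which works from the time of dosing. An event that stopped on the dosing day with no time recorded stays treatment-emergent, as does any event whose recorded dates leave the timing open.

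As a clarification only, add that a partial start date whose known month or year falls before dosing is also not treatment-emergent.

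The cost is a sentence or two of SAP text and one condition in the AE derivation program, with no new data. The small downside is that classification of these records then relies on the accuracy of the recorded stop date.
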